### 16.1.5.2 Estimation of Pharmacokinetic Parameters in Urine

For urine samples, which are collected within a time range the nominal start and end of collections times will be used for PK evaluation.

Urine concentrations which are BLQ will be set to zero.

The following urine PK parameters will be calculated for M4076 where appropriate

Symbol	Definition
$Ae_{t1-t2}$	Total amount excreted between times t1 (= start) and t2 (= end) of the current collection interval. Calculated by interval $Ae_{t1-t2} = \text{Conc} * Vu(t_{1-t2})$ and cumulative.

fe t1-t2 %	Fraction of administered drug that is excreted unchanged in urine between times t1 (= start) and t2 (= end) of the current collection interval. Calculated by interval fe t1-t2 = Aet t1-t2 /Dose and cumulative.
CL R	The renal clearance of study intervention. CL R = Ae 0-t /AUC 0-t .

Additional PK parameters may be calculated where appropriate.

## 16.1.6 Presentation of PK Concentration and PK Parameter Data

“Dose level” in the PK TFLs description refer to schedule and dose.

“Day” in the PK TFLs description refer to single dose or steady state.

### 16.1.6.1 Listings and Tables

The following PK tables will be produced (PK Analysis Set):

Part 1A + Part 1B (Day 4 predose onwards)

- Descriptive statistics of concentrations of M4076 in plasma by part, day, and dose level
- Descriptive statistics of plasma PK parameters for M4076 by part, day, and dose level (do not include diagnostic parameters).
- Descriptive statistics of dose normalized plasma PK parameters for M4076 by part, day and dose level.
- Descriptive statistics of plasma trough concentrations (Ctrough) by part and dose level, using standard descriptive statistics for Days 2, 8, 9, 22 and predose samples for subsequent cycles

Part 1B (Food effect assessment period up to Day 4 predose)

- Descriptive statistics of concentrations of M4076 in plasma by dietary status
- Descriptive statistics of plasma PK parameters and CLR for M4076 by dietary status (do not include diagnostic parameters).
- Descriptive statistics of dose normalized plasma PK parameters for M4076 by dietary status
- Descriptive statistics of amount and fraction excreted in urine by interval and cumulatively by dietary status.

The following PK Listings will be produced (Safety Analysis Set):

Part 1A + Part 1B (Day 4 predose onwards)

- Individual plasma concentrations of M4076 by part, day and dose level
- Individual plasma PK parameters for M4076 by part, day and dose level
- Individual dose normalized plasma PK parameters for M4076 by part, day and dose level
- Trough plasma concentrations (Ctrough) of M4076 by part and dose level, Days 2, 8, 9, 22 and predose samples for subsequent cycles.
- Plasma PK diagnostic parameters for M4076 by part, day and dose level
- Plasma M4076 PK sampling date, actual time, nominal time, deviation from time, percentage time deviation, concentration by participant, part and dose level status sorted in chronological order

Part 1B (Food effect assessment period up to Day 4 predose)

- Individual plasma concentrations of M4076 by dietary status
- Individual urine concentrations of M4076 by dietary status
- Individual plasma PK parameters and CLR (Part 1B) for M4076 by dietary status
- Individual dose normalized plasma PK parameters for M4076 by dietary status.
- Individual amount and fraction excreted in urine, by interval and cumulatively and dietary status.
- Plasma PK diagnostic parameters for M4076 by dietary status.
- Plasma M4076 PK sampling date, actual time, nominal time, deviation from time, percentage time deviation, concentration by participant, and dietary status sorted in chronological order
- Urine M4076 PK sampling date, start and end time and date of collection interval, urine volume, concentration, excreted amount by participant and dietary status sorted in chronological order
- Phoenix WinNonlin NCA Core Output

### 16.1.6.2 Graphical Summaries and Individual plots (PK Analysis Set)

Part 1A + Part 1B (Day 4 predose onwards)

- Individual plasma concentration versus time plots by day, and dose level; linear and semi-log; using the actual time points. If any post-dose concentration is BLQ the line representing LLOQ may be added to the semi-log plots.
- Overlaid individual (single dose and steady-state) plasma concentration versus time plots by participant, dose level, on linear and semi-log scale. If any post-dose concentration is BLQ the line representing LLOQ will be added to the semi-log plots.
- Arithmetic mean and median M4076 plasma concentration time plots; linear ( $\pm$ SD for arithmetic mean) and semi-log; using scheduled (nominal) time points by day grouped by dose level. If any post-dose concentration is BLQ the line representing LLOQ will be added to the semi-log plots
- Scatter Plot of individual dose-normalized  $AUC_{0-\infty}$ ,  $AUC_{\tau}$  and  $C_{max}$  versus Dose on a linear scale by day (single dose and steady state). Include GeoMean.
- Scatter Plot of individual  $AUC_{0-\infty}$ ,  $AUC_{\tau}$  and  $C_{max}$  versus Dose on a log-log scale. A linear regression line will be overlaid, with a pointwise confidence band for the regression line for Part 1A, Day 1 and Day 8.
- Individual  $C_{trough}$  values will be plotted against study day on a linear scale, for all participants by dose level on Days 2, 8, 9, 22 and predose samples for subsequent cycles.
- Mean  $C_{trough} \pm$ SD will be plotted by dose level, on a linear scale Days 2, 8, 9, 22 and predose samples for subsequent cycles.

Part 1B (Food effect assessment period up to Day 4 predose)

- Individual plasma concentration versus time plots by dietary status; linear and semi-log; using the actual time points. If any post-dose concentration is BLQ the line representing LLOQ may be added to the semi-log plots.
- Overlaid individual plasma concentration versus time plots (fasted and low-fat meal); linear and semi-log; using the actual time points. If any post-dose concentration is BLQ the line representing LLOQ may be added to the semi-log plots.
- Arithmetic mean and median M4076 plasma concentration time plots; linear ( $\pm$ SD for arithmetic mean) and semi-log; using scheduled (nominal) time points by dietary status. If any post-dose concentration is BLQ the line representing LLOQ will be added to the semi-log plots
- Box plot of dose-normalized  $AUC_{0-\infty}$ ,  $AUC_{0-tlast}$ ,  $AUC_{\tau}$  and  $C_{max}$  by dietary status.

- Plot of Mean (+/- SD) Cumulative Amount of M4076 Excreted in Urine versus Mid time interval on a Linear Scale by dietary status
- Plot of Individual Cumulative Amount of M4076 Excreted in Urine versus Mid time interval on a Linear Scale by dietary status

CCI

CCI

CCI

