^c Efforts should be made to collect blood for PK and CCl [REDACTED] and biopsy samples around similar time points (± 20 minutes).

Cl

Period 1 Day 8/9 PK sampling may be conducted on Day 15/16, or Period 2 Day 1/2, if required for logistical reasons and/or in case study intervention was interrupted and resumed. In this case, timing of associated triplicate ECG measurements should be rescheduled accordingly, and the Sponsor notified in advance.

Table 4

Part 1B Preliminary Food Effect Assessment: Pharmacokinetic, ECG and CCI Assessments

Study Day	M4076 Dosing	PK Sampling Time	Urine Collection for PK	ECG ^b	Paired Biopsies	CCI
Screening (D -28 to -8)					X	
-7	X	Predose ^a	X (1 hour, 0)	X		
		0.5 hour ± 10 minutes postdose	X (0 to 4 hours)			
		1 hour ± 10 minutes postdose		X		
		2 hours ± 10 minutes postdose		X		
		3 hours ± 20 minutes postdose		X		
		4 hours ± 20 minutes postdose	X (4 to 8 hours)	X		
		6 hours ± 20 minutes postdose		X		
		8 hours ± 20 minutes postdose	X (8 to 24 hours)	X		
		10 hours ± 20 minutes postdose				
-6		24 hours ± 2 hours postdose	X (24 to 48 hours)			
-5		48 hours ± 2 hours postdose	X (48 to 72 hours)			
-4		72 hours ± 2 hours postdose				
Day -3 to -1 Washout						

Study Day	M4076 Dosing	PK Sampling Time	Urine Collection for PK	ECG ^b	Paired Biopsies	CCI
Day 1	X	Predose ^a		X		
		0.5 hour ± 10 minutes postdose	X (0 to 4 hours)			
		1 hour ± 10 minutes postdose				
		2 hours ± 10 minutes postdose		X		
		3 hours ± 20 minutes postdose		X		
		4 hours ± 20 minutes postdose	X (4 to 8 hours)	X		
		6 hours ± 20 minutes postdose		X		
		8 hours ± 20 minutes postdose	X (8 to 24 hours)	X		
		10 hours ± 20 minutes postdose				
Day 2		24 hours ± 2 hours postdose	X (24 to 48 hours)			
Day 3		48 hours ± 2 hours postdose	X (48 to 72 hours)			
Day 4 ^d	X	Predose ^a				
		1 hours ± 10 minutes postdose				
		3 hours ± 60 minutes postdose			X ^c	
		6 hours ± 20 minutes postdose				
		8 hours ± 20 minutes postdose				

ECG = electrocardiogram; γ-H2AX = gamma histone family member X; Pd = pharmacodynamic; PK = pharmacokinetic; RDE = recommended dose for evaluation.

^a All predose samples have a window of – 60 minutes prior to next dosing.

- d** Triplicate ECG collection is only applicable to participants dosed in the fasted state. The fasting window in Part 1B is defined as 10 hours predose to 4 hours postdose.

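### The two Part 1B plots of cumulative urinary excretion use the midpoint of each collection interval as the x-value; a cumulative amount belongs at the interval end (minor, two descriptive figures)

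*SAP*

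**What the plan says.** SAP 16.1.6.2, under the Part 1B food-effect figures, specifies two urine plots: "Plot of Mean (+/- SD) Cumulative Amount of M4076 Excreted in Urine versus Mid time interval on a Linear Scale by dietary status" and "Plot of Individual Cumulative Amount of M4076 Excreted in Urine versus Mid time interval on a Linear Scale by dietary status". Both pair a cumulative quantity with the mid-time of the interval.

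SAP 16.1.5.2 defines the amount excreted, Ae, as the "Total amount excreted between times t1 (= start) and t2 (= end) of the current collection interval", to be given per interval and cumulatively. It derives renal clearance as Ae over 0 to t divided by AUC over 0 to t. On timing it states: "For urine samples, which are collected within a time range the nominal start and end of collections times will be used for PK evaluation".

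The intervals are in protocol Section 1.3.3, Table 4. After each of the two single doses, urine is collected over 0-4, 4-8, 8-24, 24-48 and 48-72 h; the two longest entries read "X (24 to 48 hours" and "X (48 to 72 hours". A predose collection is marked before the Day -7 dose only.

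**The concern.** A cumulative amount through an interval is known, and has been reached, only at the end of that interval. Placing it at the midpoint moves every point to the left. A midpoint is the usual x-value for an excretion rate (Ae divided by interval length), but no rate plot appears in the readable text.

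Followed as written, the figures would show the full 0-72 h amount at 60 h, while the last collection is still running. Early excretion would look faster than it was, and the plateau would seem to arrive sooner. The mean plasma curves are to be drawn at nominal sampling times, so plasma and urine curves in the same report would be out of step by up to 12 h. In the readable text these are the only figures of the urinary time course.

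**Working it through.** **Inputs.** Interval starts and ends come from protocol Table 4. SAP 16.1.5.2 uses nominal times. The plan states no figure of its own to reproduce.

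**Shift.** Midpoint = (start + end)/2. Shift = end − midpoint = half the interval width.

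**Slope.** For each segment, the cumulative increment is the same on either axis, so the ratio of plotted to correct slope is (difference between end times)/(difference between midpoints), with the origin at (0,0).

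| Interval (h) | Plotted at (h) | Reached at (h) | Shift (h) | Slope ratio of segment ending here |
|---|---|---|---|---|
| 0-4 | 2 | 4 | 2 | 4/2 = 2.0 |
| 4-8 | 6 | 8 | 2 | (8−4)/(6−2) = 1.0 |
| 8-24 | 16 | 24 | 8 | (24−8)/(16−6) = 1.6 |
| 24-48 | 36 | 48 | 12 | (48−24)/(36−16) = 1.2 |
| 48-72 | 60 | 72 | 12 | (72−48)/(60−36) = 1.0 |

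These results need no assumption about kinetics. The first ratio does depend on the origin. If the Day -7 predose collection, read as the hour before dosing, were plotted at −0.5 h with amount zero, the first ratio would be (1/2.5)/(1/4) = 1.6. Day 1 has no predose urine collection, so (0,0) is the natural start there.

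**Illustration in amounts.** The documents give no half-life. As an assumption only, take first-order excretion without an absorption phase, with cumulative fraction of the eventual amount = 1 − 2^(−t/half-life) and half-lives of 4, 12 and 24 h. Each cell gives the value that would be drawn, then the true value at that time.

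| Drawn at | 4 h half-life | 12 h half-life | 24 h half-life |
|---|---|---|---|
| 2 h | 50.0% vs 29.3% | 20.6% vs 10.9% | 10.9% vs 5.6% |
| 16 h | 98.4% vs 93.8% | 75.0% vs 60.3% | 50.0% vs 37.0% |
| 36 h | 100.0% vs 99.8% | 93.8% vs 87.5% | 75.0% vs 64.6% |
| 60 h | 100.0% vs 100.0% | 98.4% vs 96.9% | 87.5% vs 82.3% |

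At 2 h the drawn amount is 1.71 to 1.94 times the true amount across these half-lives. By 60 h the gap is about 0 to 5 percentage points.

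**The case against.** The strongest reply is that nothing is estimated or decided from these plots. That stands:

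- Ae, the fraction excreted and renal clearance are computed from interval start and end times, not midpoints.
- The food-effect model in SAP 16.1.3 uses plasma AUC and Cmax only.
- Fed and fasted periods share the same nominal post-dose intervals, so both curves move equally and their comparison at each plotted point is unchanged.
- SAP 16.1.6.1 also plans tables and listings of the amount and fraction excreted, per interval and cumulative, and a listing with collection start and end times. The correct time course is therefore available in the report.
- The secondary endpoint is urine PK parameters such as renal clearance, if the data permit. An excretion-time figure is not a named endpoint.

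It can also be said that the SAP refers to table and figure shells that are not available here, so what would be programmed is unverified. That is fair, but no readable text moves the points to the interval end, and the same axis is written in both bullets.

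A reader might infer more than the documents support:

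- *That the plan doubles the excretion rate.* It derives no rate. The doubling applies only to the visual slope of the first segment from (0,0); two of the five segments have no slope error.
- *That the error is worst where intervals are long.* This is true only of the horizontal shift. In slope, the worst segment is a 4 h interval, and the last 24 h interval has no slope error. In amount, under the assumed 12 h half-life, the gap is about 9.7 points at 2 h and 1.6 points at 60 h.
- *That renal clearance or the food-effect result is biased.* Neither uses the plotted x-value.

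**Conclusion.** The axis is wrong as written, and the error is minor. In both plots the cumulative amounts are drawn 2, 2, 8, 12 and 12 h too early. The curve's shape also changes: the first segment is twice as steep as the true 0-4 h mean rate if the curve starts at (0,0), and later segments are 0% to 60% too steep. The shifts rest only on the protocol's nominal intervals; the doubling also rests on the (0,0) origin. The percentages by half-life are illustrative. The consequence is limited to two descriptive figures, from which a reader could misjudge how early M4076 is excreted. No tabulated result or planned comparison changes.

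**What to change.** In both urine bullets of SAP 16.1.6.2, replace the interval mid-time with the end time of the collection interval (4, 8, 24, 48 and 72 h), and state that the curves start at (0,0). Make the same change in the figure shells if they carry this axis. Use midpoints only if an excretion-rate plot (Ae divided by interval length) is added.

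The cost is a few words in two bullets and one plotting variable. It needs no new data and changes no other output.

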## Appendices

18.1 **Appendix 1 – NCI-CTC Gradable and Non-Gradable Safety Laboratory Test Parameters and Direction(s) of Abnormality****Table 7** **Protocol-Required Clinical Laboratory Assessments**

Laboratory Assessments	Parameters					
Hematology	Platelet count	Mean corpuscular volume (MCV)	White Blood Cell Count with absolute and percentage (%): • Neutrophils • Lymphocytes • Monocytes • Eosinophils • Basophils			
	Reticulocytes					
	Hemoglobin	Mean corpuscular hemoglobin (MCH)				
	Hematocrit					
Coagulation	INR, prothrombin time, partial thromboplastin time (aPTT)					
Biochemistry	Blood Urea Nitrogen and/or Urea	Potassium	Aspartate aminotransferase	Bilirubin (total and direct)		
	Creatinine	Sodium	Alanine aminotransferase	Protein and albumin		
	Glucose	Calcium	Alkaline phosphatase			
	Gamma glutamyltransferase (gGT)	Lipase	Amylase			
Details of liver chemistry stopping criteria and required actions are given in protocol Section 6.6.1 and Appendix 5 of the protocol.						
Routine Urinalysis	
 
Specific gravity
 
pH, glucose, protein, blood, ketones by dipstick
 
Microscopic examination (if blood or protein is abnormal)
 
					
Other Screening Tests	
 
Serum and urine human chorionic gonadotropin pregnancy test (as needed for women of childbearing potential).
 
 
Serology (with no preclinical signs of hepatotoxicity, hepatitis B surface antigen, hepatitis C virus antibody) to rule out active infection will be performed at the Investigator's discretion. HIV screening is optional at the Investigator's discretion unless required locally.
 
All study-required laboratory assessments will be performed by a central laboratory, except for safety laboratory assessments.
					

**Table 8** NCI-CTC gradable parameters

Laboratory Assessment	Parameters	Name in NCI-CTC	Direction(s) of abnormality
Hematology	Hemoglobin	Anemia/Hemoglobin increased	Low/High
	Leukocytes (WBC)	White blood cell decreased / Leukocytosis	Low/High
	Neutrophils	Neutrophil count decreased	Low
	Lymphocytes	Lymphocyte count decreased / increased	Low/High
	Eosinophils	Eosinophila [a]	High
	Platelets	Platelet count decreased	Low
Biochemistry	Albumin	Hypoalbuminemia	Low
	Alanine Aminotransferase (ALT)	Alanine Aminotransferase increased [a]	High
	Aspartate Aminotransferase (AST)	Aspartate Aminotransferase increased [a]	High
	Alkaline Phosphatase	Alkaline Phosphatase increased [a]	High
	Gamma Glutamyl Transferase (GGT)	GGT increased [a]	High
	Total Bilirubin	Blood bilirubin increased [a]	High
	Amylase	Serum amylase increased	High
	Lipase	Lipase increased	High
	Creatinine	Creatinine increased [a]	High
	Sodium	Hyponatremia / Hypernatremia	Low / High
	Potassium	Hypokalemia / Hyperkalemia	Low / High
	Calcium	Hypocalcemia / Hypercalcemia	Low / High
Coagulation	Activated Partial Thromboplastin Time	Activated Partial Thromboplastin Time prolonged	High
	Prothrombin Intl. Normalized Ration (INR)	INR increased	High

Note: parameters with both Low and High directions of abnormality are going to be split. For example, Calcium is going to be split in Calcium Low and Calcium High.

a on-treatment grading dependent on baseline status.

**Table 9** NCI-CTC non-gradable parameters

Laboratory Assessment	Parameters
Hematology	Hematocrit Mean corpuscular volume (MCV) Mean corpuscular hemoglobin (MCH) Reticulocytes Reticulocytes/Erythrocytes Neutrophils/Leukocytes (%) Lymphocytes/Leukocytes (%) Basophils Basophils/Leukocytes (%) Eosinophils/Leukocytes (%) Monocytes Monocytes/Leukocytes (%)
Biochemistry	Total Protein Urea Nitrogen (BUN) Serum cystatin C
Coagulation	Prothrombin Time Prothrombin Time/Standard
Urinalysis	Blood Bacteria (Microscopic analysis) Casts (Microscopic analysis) Crystals (Microscopic analysis) Epithelial Cells (Microscopic analysis) Bilirubin Glucose in Urine Urobilinogen Ketones Nitrite pH Proteins in Urine Erythrocytes in Urine (Microscopic analysis) Leukocytes esterase Leukocytes in Urine (Microscopic analysis) Specific gravity

